11.3 Analysis of Laboratory Data

Changes from Baseline and Maintenance Baseline in continuous laboratory parameters will be summarized by n, mean, standard deviation, minimum value, median, and maximum value for each treatment group in the Maintenance Study. Treatment group differences for changes from Baseline will be analyzed using a one-way Analysis of Variance (ANOVA) and 95% CI for treatment difference will be presented for selected laboratory parameters.

Shift tables from Baseline to the final value (the last assessment during each treatment period) according to the normal range will be provided for each hematology, clinical chemistry parameter and urinalysis parameter. The laboratory data will be categorized as low, normal, or high based on the normal ranges of the laboratory used in this study. The shift tables will tabulate the number and percentage of subjects with Baseline values within/above the normal range versus final and post-baseline values below the normal range and with Baseline values below/within the normal range versus final and post-baseline values above the normal range.

For selected laboratory parameter with Common Toxicity Criteria (CTC), the number and percentage of subjects with any laboratory determinations meeting CTC Version 3.0 (or later) of Grade ≥ 3 , as well as being a higher grade than the Baseline grade, will be summarized. For each of these subjects, the whole course of the laboratory parameters with CTC Grade ≥ 3 will be listed.

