6.0 Analysis Conventions

Definition of Induction Baseline

The induction baseline (hereafter referred to as Baseline) visit date is the date when the first dose of study drug is received during Induction Study and referred to as Day 1 or Week 0. The baseline value for a variable is defined as the last non-missing value on or before the date of the first dose of study drug during Induction Study.

Definition of Maintenance Baseline

The maintenance baseline visit date is the date when the first dose of study drug is received during Maintenance Study. The maintenance baseline value for a variable is defined as the last non-missing value on or before the date of the first dose of study drug during Maintenance Study.

Definition of Final Observation

Final Observation in Maintenance Study is defined as the last non-missing observation collected within 70 days following the last dose of study drug for subjects who are re-randomized. The 70-day follow-up phone call will not be required for any subject who initiates commercial adalimumab.

Definition of Rx Days (Days Relative to the First Dose of Maintenance Study Drug)

Rx Day during the Maintenance Study is calculated as the event date minus the date of first dose of the Maintenance Study drug plus 1. The Rx Day will be a negative value

when the time point of interest is prior to the date of first dose of study drug, and the Rx Day will be a positive value when the time point of interest is after the first dose date. Rx days are used to map actual study visits to the protocol specified study visits during Maintenance Study, as defined below. If a subject has not taken any study drug during Maintenance Study, Rx Day during the Maintenance Study will be calculated as the event date minus the date of re-randomization date plus 1.

Definition of Analysis Windows

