11.3.2 Hy's Law Cases

According to FDA's Guidance for Industry "Drug-Induced Liver Injury: Premarketing clinical evaluation" (July 2009), when aminotransferase (AT) abnormalities indicating hepatocellular injury are accompanied by evidence of impaired hepatic function (bilirubin elevation $> 2 \times$ ULN), in the absence of evidence of biliary obstruction (i.e., significant elevation of ALP) or some other explanation of the injury (e.g., viral hepatitis, alcohol hepatitis), the combined finding (i.e., Hy's Law cases) represents a signal of a potential for the drug to cause severe DILI.

For the purpose of assessing for potential Hy's law cases, the frequencies and percentages of subjects with post baseline liver specific function test values that meet the following criteria of potential clinical interest will be summarized by treatment group:

- $ALT \geq 3 \times$ ULN
- $ALT \geq 5 \times$ ULN
- $ALT \geq 10 \times$ ULN
- $ALT \geq 20 \times$ ULN

- $\text{AST} \geq 3 \times \text{ULN}$
- $\text{AST} \geq 5 \times \text{ULN}$
- $\text{AST} \geq 10 \times \text{ULN}$
- $\text{AST} \geq 20 \times \text{ULN}$
- $\text{TBL} \geq 2 \times \text{ULN}$
- $\text{Alkaline phosphatase} \geq 1.5 \times \text{ULN}$
- $\text{ALT and/or AST} \geq 3 \times \text{ULN}$ and concurrent $\text{TBL} \geq 1.5 \times \text{ULN}$
- $\text{ALT and/or AST} \geq 3 \times \text{ULN}$ and concurrent $\text{TBL} \geq 2 \times \text{ULN}$

A listing of potentially clinically significant liver function laboratory values will be provided. The listing will include all subjects who met any of the following 4 criteria:

- $\text{ALT} \geq 2.5 \times \text{ULN}$, or
- $\text{AST} \geq 2.5 \times \text{ULN}$, or
- $\text{Alkaline Phosphatase} \geq 2.5 \times \text{ULN}$, or
- $\text{Total Bilirubin} \geq 1.5 \times \text{ULN}$.

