11.3 Analysis of Laboratory Data

All laboratory data collected after first dose of Maintenance Study drug will be excluded from this analysis.

Changes from Baseline in continuous laboratory parameters will be summarized by n, mean, standard deviation, minimum value, median, and maximum value for each treatment group in the Induction Study. Treatment group differences for changes from Baseline will be analyzed using a one-way Analysis of Variance (ANOVA) and 95% CI for treatment difference will be presented for selected laboratory parameters.

Shift tables from Baseline to the final value (the last assessment during each treatment period) according to the normal range will be provided for each hematology, clinical chemistry parameter and urinalysis parameter. The laboratory data will be categorized as low, normal, or high based on the normal ranges of the laboratory used in this study. The shift tables will tabulate the number and percentage of subjects with Baseline values within/above the normal range versus final and post-baseline values below the normal range and with Baseline values below/within the normal range versus final and post-baseline values above the normal range.

For selected laboratory parameter with Common Toxicity Criteria (CTC) a listing of all subjects with any laboratory determinations meeting CTC Version 3.0 (or later) of Grade ≥ 3 will be provided. For each of these subjects, the whole course of the parameter will be listed. For subjects with laboratory values with CTC Grade ≥ 3 , all of the laboratory parameters for those subjects will be listed.

11.3.1**Assessment of Shifts from Baseline in Liver-Specific Laboratory Variables**

Baseline and post-baseline liver-specific laboratory will be categorized as follows:

< 1.5 times the upper limit of the reference range

≥ 1.5 to < 3 the upper limit of the reference range

≥ 3 to < 5 the upper limit of the reference range

≥ 5 to < 8 the upper limit of the reference range

≥ 8 the upper limit of the reference range

For each variable, shift tables will be generated that cross tabulate the subjects' as deemed appropriate:

Category of the baseline value versus category of the final value,

Category of the baseline value versus maximum category

Note that the maximum category is used, rather than the category of the maximum values. The two may be different due to variation in the reference range.

No statistical tests will be performed for this analysis.

11.3.2**Hy's Law Cases**

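### Maintenance laboratory abnormalities are judged against Week 0 with no stated start at the first maintenance dose, so abnormalities that arose in induction can be counted under the eow or ew arm

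*SAP*

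**What the plan says.** The Maintenance SAP, Section 6.0, has two reference points. The first is Week 0: "The induction baseline (hereafter referred to as Baseline) visit date is the date when the first dose of study drug is received" in induction, and the same paragraph ties a variable's baseline value to that date. The second is separate: "The maintenance baseline visit date is the date when the first dose of study drug is received during Maintenance Study".

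Section 11.3 uses Maintenance Baseline once, for the descriptive summary of continuous changes. The other items there refer to Baseline:

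- the between-arm one-way ANOVA is on change from Baseline;
- the normal-range tables are described as "Shift tables from Baseline to the final value (the last assessment during each treatment period", with further cells for post-baseline values;
- the CTC item counts subjects with "any laboratory determinations meeting CTC Version 3.0 (or later" versions) at Grade 3 or higher, "as well as being a higher grade than the Baseline grade".

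Section 11.3.1 cross-tabulates the category of the baseline value against the final and the maximum category. Section 11.3.2 summarizes "the frequencies and percentages of subjects with post baseline liver specific function test values" that exceed fixed multiples of the upper limit of normal.

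The Induction SAP, Section 11.3, opens with a cut: "All laboratory data collected after first dose of Maintenance Study drug will be excluded from this analysis". The Maintenance SAP has no counterpart that removes induction data.

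**The concern.** Subjects are re-randomized to eow or ew at Week 8. An abnormality that began before that cannot be an effect of the maintenance arm, yet the wording allows it to be reported under one. The Maintenance SAP handles adverse events differently: Section 11.2.1 starts them at the first maintenance dose and ends them 70 days after the last. The laboratory and adverse event tables of one report could then cover different periods.

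This bears on a planned comparison. Section 11.1 calls for two-sided tests of eow against ew at 0.05, with Fisher's exact test for categorical safety variables unless otherwise specified. Some carried-over abnormalities may reflect the induction regimen (720 mg versus 320 mg in total, Section 4.2) and not the maintenance regimen under test.

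**Working it through.** **Which values count.** The SAP states no figure on this point, so there is nothing to reproduce. Four hypothetical subjects, shown by CTC grade, illustrate the rule in 11.3. Week 4 is an induction visit. Table 1 of the Maintenance SAP places values up to Rx Day 1 at Maintenance Baseline and opens its first later window on Day 2.

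| Subject | Week 0 | Week 4 | Week 8 | Maintenance | Counted, literal reading | Counted if only Rx Day 2 onward is used | New in maintenance |
|---|---|---|---|---|---|---|---|
| A | 1 | 3 | 1 | 1 | yes | no | no |
| B | 1 | 3 | 3 | 3 | yes | yes | no |
| C | 3 | 1 | 1 | 3 | no | no | yes |
| D | 1 | 1 | 1 | 3 | yes | yes | yes |

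Subject A depends on how the text is read. Subjects B and C are misclassified under either reading, because the comparison is with Week 0.

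**Item by item.**

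- CTC count: Week 0 reference, and no start or end for the values.
- Normal-range shift tables: Week 0 reference. The final value is limited to the treatment period, but the post-baseline cells are not.
- Liver shift tables: Week 0 reference, and no start for the maximum category.
- Between-arm ANOVA: Week 0 reference only.
- Potential Hy's law counts: fixed multiples of the upper limit, so there is no baseline comparison. Only the missing start and end apply.

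**Illustration of size.** The event rates below are assumptions.

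- Arm size: 840 × 2/5 + 100/2 = 336 + 50 = 386 at most (2:2:1 in the Main Study, 1:1 in Japan, no attrition). A Japan arm has 50.
- m = probability of an abnormality that is new in maintenance: 2% for eow, 4% for ew.
- q = probability of being counted because of an induction-onset abnormality, taken as equal in both arms and independent of m.
- Counted rate = 1 − (1 − m)(1 − q).
- Difference = (0.04 − 0.02)(1 − q).
- Extra subjects in the eow arm = n × q × 0.98.
- Power: two-sided 5% normal-approximation test of two proportions, 386 per arm.

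| q | eow | ew | Ratio | Difference | Extra, integrated eow arm | Extra, Japan eow arm | Power |
|---|---|---|---|---|---|---|---|
| 0 | 2.00% | 4.00% | 2.00 | 2.00 points | 0 | 0 | 37% |
| 1% | 2.98% | 4.96% | 1.66 | 1.98 points | 3.8 | 0.5 | 29% |
| 2% | 3.96% | 5.92% | 1.49 | 1.96 points | 7.6 | 1.0 | 24% |
| 4% | 5.92% | 7.84% | 1.32 | 1.92 points | 15.1 | 2.0 | 18% |

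Example for q = 2%: eow 1 − 0.98 × 0.98 = 0.0396; ew 1 − 0.96 × 0.98 = 0.0592; 0.0592/0.0396 = 1.49.

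To place q: the Induction SAP's Table 1 has four visits after Week 0. At an assumed 0.5% chance per visit, 1 − 0.995^4 = 2.0%. That is q under the literal reading. If Table 1 of the Maintenance SAP limits the data, only abnormalities persisting after Day 1 contribute, and q is smaller by an unknown amount.

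**The case against.** Several points on the other side are sound.

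- **Scope of the data.** A reader might infer that every induction value from Weeks 1 to 8 enters the maintenance tables. The documents do not settle that. The SAP is written solely for the maintenance sub-study, its Table 1 gives induction values no slot after entry, and the shift-table final value is tied to the treatment period. The literal reading is only one reading. However, Section 11.3 does not say that Table 1 limits the *any*, *maximum category* or *post baseline* values, and subjects B and C do not depend on it.
- **Hy's law.** It is tempting to say that all liver abnormalities are defined against Week 0. The criteria in 11.3.2 are not.
- **Bias.** A reader might infer that the ew versus eow contrast is biased. Re-randomization is stratified by induction regimen and Week 8 response (Section 5.2), so carried-over abnormalities balance in expectation and the risk difference hardly moves. For the ANOVA, either reference gives an unbiased arm difference; which is more precise depends on correlations that the documents do not give. Chance imbalance matters most at about 50 per Japan arm.
- **Double counting.** The same event need not be counted in both reports. For CTC grades the Induction SAP plans only a listing. Overlap is possible for the shift and liver tables.
- **Value of Week 0.** All subjects receive adalimumab from Week 0, so Week 0 is the only reference before study treatment. Dropping it would hide drug-related abnormalities that began in induction and persisted. This is a good reason to keep Week 0 alongside the other reference, not to use it alone.
- **Existing mitigation.** Continuous changes are already summarized from Maintenance Baseline, though only descriptively, and the liver shift tables carry no tests.

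**Conclusion.** The point holds in a limited form. The CTC count, the normal-range and liver shift tables and the between-arm ANOVA are referenced to Week 0, and several counted values have no stated start at the first maintenance dose. Both features differ from the adverse event rule in the same SAP and from the cut in the Induction SAP. Abnormalities that began in induction and persisted can be attributed to a maintenance arm, and recurrences at the Week 0 grade are lost. Read literally, abnormalities that resolved before Week 8 can enter too.

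The consequence is inflated absolute rates, a diluted ratio and some lost power, without systematic bias toward eow or ew. The documents do not give its size. The 1.66 to 1.32 range for a true ratio of 2.0 rests wholly on assumed rates and on full retention to re-randomization; the loss from recurrences is not quantified. The change is worth making because it improves attribution of the between-arm safety results at little cost.

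**What to change.** In Sections 11.3, 11.3.1 and 11.3.2 of the Maintenance SAP, add a sentence stating that counted values are those after the first maintenance dose and within 70 days of the last dose. This matches the end already used for adverse events and for Final Observation.

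Report the CTC Grade 3 or higher count, the normal-range and liver shift tables and the between-arm change analysis against Maintenance Baseline as well as against Week 0, and base the ew versus eow comparison on Maintenance Baseline. For the potential Hy's law counts, only the start and end rule is needed.

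Both reference points are already defined in Section 6.0, so no new derivation is required. The cost is about one sentence per subsection and one additional set of tables.

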11.3.1 Assessment of Shifts from Baseline in Liver-Specific Laboratory Variables

Baseline and post-baseline liver-specific laboratory will be categorized as follows:

- < 1.5 times the upper limit of the reference range;
- $\geq 1.5 \times$ to < 3 the upper limit of the reference range;

- ≥ 3 to < 5 the upper limit of the reference range;
- ≥ 5 to 8 and the upper limit of the reference range;
- ≥ 8 the limit of the reference range.

For each variable, shift tables will be generated that cross tabulate the subjects' as deemed appropriate:

- Category of the baseline value versus category of the final value,
- Category of the baseline value versus maximum category

Note that the maximum category is used, rather than the category of the maximum values. The two may be different due to variation in the reference range.

No statistical tests will be performed for this analysis.

11.3.2 Hy's Law Cases

According to FDA's Guidance for Industry "Drug-Induced Liver Injury: Premarketing clinical evaluation" (July 2009), when aminotransferase (AT) abnormalities indicating hepatocellular injury are accompanied by evidence of impaired hepatic function (bilirubin elevation $> 2 \times$ ULN), in the absence of evidence of biliary obstruction (i.e., significant elevation of ALP) or some other explanation of the injury (e.g., viral hepatitis, alcohol hepatitis), the combined finding (i.e., Hy's Law cases) represents a signal of a potential for the drug to cause severe DILI.

For the purpose of assessing for potential Hy's law cases, the frequencies and percentages of subjects with post baseline liver specific function test values that meet the following criteria of potential clinical interest will be summarized by treatment group:

- $ALT \geq 3 \times$ ULN
- $ALT \geq 5 \times$ ULN
- $ALT \geq 10 \times$ ULN
- $ALT \geq 20 \times$ ULN

- $\text{AST} \geq 3 \times \text{ULN}$
- $\text{AST} \geq 5 \times \text{ULN}$
- $\text{AST} \geq 10 \times \text{ULN}$
- $\text{AST} \geq 20 \times \text{ULN}$
- $\text{TBL} \geq 2 \times \text{ULN}$
- $\text{Alkaline phosphatase} \geq 1.5 \times \text{ULN}$
- $\text{ALT and/or AST} \geq 3 \times \text{ULN}$ and concurrent $\text{TBL} \geq 1.5 \times \text{ULN}$
- $\text{ALT and/or AST} \geq 3 \times \text{ULN}$ and concurrent $\text{TBL} \geq 2 \times \text{ULN}$

A listing of potentially clinically significant liver function laboratory values will be provided. The listing will include all subjects who met any of the following 4 criteria:

- $\text{ALT} \geq 2.5 \times \text{ULN}$, or
- $\text{AST} \geq 2.5 \times \text{ULN}$, or
- $\text{Alkaline Phosphatase} \geq 2.5 \times \text{ULN}$, or
- $\text{Total Bilirubin} \geq 1.5 \times \text{ULN}$.

11.4 Analysis of Vital Signs and Weight

The following vital signs are measured at every visit during the Maintenance Study.

- Body Weight [kg]
- Blood Pressure (Systolic/Diastolic) [mmHg]
- Pulse (bpm)
- Respiratory Rate (RPM)
- Temperature [$^{\circ}\text{C}$]

Changes from Baseline in vital sign values will be summarized by n, mean, standard deviation, minimum value, median, and maximum value for each treatment group.

Treatment group differences for changes from Baseline will be analyzed using a one-way Analysis of Variance (ANOVA) and 95% CI for treatment difference will be presented.

The number and percentage of subjects meeting the criteria for potentially clinically significant (PCS) vital sign values will also be summarized.

The criteria for potentially clinically significant vital sign findings are presented in [Table](#).

Table 8. Criteria for Potentially Clinically Significant Vital Sign Findings

Vital Sign	Category	Criteria for Potential Clinically Significant Vital Signs
Systolic blood pressure	Low	Value \leq 90 mmHg and/or decrease \geq 20 mmHg from Baseline
	High	Value \geq 180 mmHg and/or increase \geq 20 mmHg from Baseline
Diastolic blood pressure	Low	Value \leq 50 mmHg and/or decrease \geq 15 mmHg from Baseline
	High	Value \geq 105 mmHg and/or increase \geq 15 mmHg from Baseline
Pulse	Low	Value \leq 50 bpm and/or decrease \geq 15 mmHg from Baseline
	High	Value \geq 120 mmHg and/or increase \geq 15 mmHg from Baseline

Vital sign results meeting the criteria for PCS findings will be identified in a listing.

12.0 Summary of Changes

This is the first version of the SAP for 44-Week Double-Blind Maintenance Japan Sub-Study.

12.1 Summary of Changes Between the Latest Version of Protocol and the Current SAP

The statistical changes between current SAP and the latest version of protocol are listed below:

- Added two endpoints in the additional efficacy analysis (Section 10.4):
 - proportion of subjects with IBDQ total score \geq 170 over time.
 - proportion of subjects with fecal calprotectin below 150 mg/kg over time.
- Updated the rules for efficacy assessment based on concomitant medication per latest analysis conventions for immunology clinical studies. Only UC-related systemic or rectal corticosteroids will be used for censoring purpose

and will have last non-missing value prior to censoring carried forward for non-categorical assessments from that point forward.

- The following two IBDQ-related endpoints have been added as ranked #13 and #14 secondary endpoints (Section 10.3) for the Maintenance Study. The addition of these two ranked secondary endpoints is based on recent FDA's feedback from Upadacitinib UC program to consider specific questions or domains within IBDQ that are most relevant to IBD patients.
 - Proportion of Week 8 responders (per Full Mayo score) with response in IBDQ Bowel Symptom domain (increase of IBDQ bowel symptom domain score ≥ 6 from Baseline) at Week 52.
 - Proportion of Week 8 responders (per Full Mayo score) with response in IBDQ fatigue item (increase of IBDQ fatigue item score ≥ 1 from Baseline) at Week 52.

12.2 Summary of Changes Between the Previous Version and the Current Version of the SAP

This is the first version of the SAP for the 44-Week Double-Blind Maintenance Japan Sub-Study.

13.0 Appendix

None.

3.0 Introduction

This statistical analysis plan (SAP) describes the statistical analysis for Japan sub-study to be completed by the AbbVie Global Statistics Department for study Protocol M14-033 Amendment 3 dated 16 June 2016. It provides details to further elaborate statistical methods as outlined in the protocol and describes analysis conventions to guide the statistical programming work.

This is the first version of SAP for the 8-Week Double-Blind Induction Study of Protocol M14-033 for Japan sub-study.

Study M14-033 consists of a main study and a Japan sub-study. This SAP version is developed solely for the Induction Japan Sub-Study following the Protocol Amendment 3.

This analysis plan describes the primary and secondary efficacy analyses as well as the safety analysis for the Induction Japan Sub-Study under the Protocol Amendment 3.

Unless noted otherwise, all analyses will be performed using SAS version 9.4 or later (SAS Institute Inc., Cary, NC 27513) under the UNIX operating system.

4.0 Study Objectives, Design and Procedures

4.1 Objectives for Japan Sub-Study

The study objective for Japan Sub-Study is to evaluate the safety and efficacy of higher induction and maintenance dosing regimens in subjects with moderately to severely active ulcerative colitis and to show the consistency of efficacy between Japanese population and integrated population of Japanese and western subjects.

